Digital storytelling intervention. The digital intervention package, which is 12 minutes long, includes a brief introduction by an RHCP community partner, four stories with transitions, and a short closing educational message re-enforcing the four diabetes self-management behavioral goals (healthful diet, physical activity, medication adherence, glucose self-monitoring). The storytellers include two women and two men; they reflect some of the heterogeneity among Hispanic/Latino subgroups (two Mexican, one Central American, and one South American) in the U.S. After obtaining consent in the clinical setting or over the phone, study staff will deliver the intervention in the exam room, a separate private room or provide patient with a web address to view the video on YouTube from home.

Following the video exposure, study staff will ask these questions to each participant and record their answers: 1) What is your reaction to the video?, 2) What was the main message of the video, and 3) Does the video motivate you to make any changes to the way you manage your diabetes (probe positive responses)? These questions will confirm participant receipt of the intervention, which is an important fidelity construct to ensure that participants received and understood the intervention¹⁰¹.

Participants will be offered a copy of the video as a portable storage device (i.e., “flash drive”) for viewing on a computer, a DVD for viewing on a television, or a web address to watch the video on YouTube. Participants will also be provided access to the storytelling intervention as an application on their mobile phones and/or tablets. In our pilot of the storytelling intervention, all participants cited the use of mobile smart phones. Study staff will offer to assist participants in downloading this application during the baseline visit, and encourage participants to watch the video with family members or friends within their support network.

Figure 3. Still images from the existing digital storytelling intervention

Rationale for implementation in the clinical setting. The work proposed in this application is intentionally placed on the boundary of the efficacy-to-effectiveness transition¹⁰² in clinical trials. We considered conducting a more traditional efficacy study, where participants would be invited to separate study visits for intervention delivery and measurements. However, interventions that target improvements in diabetes self-management behaviors cannot be easily disarticulated from the clinical setting. The hypothesized patient activation that may occur as a result of exposure to the digital storytelling intervention requires interaction with their healthcare home in order to translate that activation into improved outcomes. Therefore, we pilot tested the intervention in primary care-based clinical settings. We demonstrated feasibility of this approach while adapting intervention implementation for both sites.

Mobile short message service. Mobile short message service, i.e., text messaging, has been shown to have some impact on diabetes self-care¹⁰⁴ and cardiovascular-related lifestyle¹⁰⁵ behaviors. Furthermore, a Cochrane review suggested moderate evidence for increasing self-efficacy for diabetes self-management using mobile phone messaging¹⁰⁶. Therefore, to increase the likelihood that participants will watch the storytelling video several times during the intervention interval, participants will receive a monthly automated text message (five total) that asks them to self-rate their motivational level and self-efficacy for managing their T2D (0 = no motivation/self-confidence to 10 = extremely motivated/confident), and will recommend that they watch the storytelling intervention if they score lower than a 7. The rationale for the addition of mobile messages is that this intervention augmentation re-enforces concepts consistent with our theoretical framework. It increases

the potential treatment dose while maintaining an intervention package that is highly scalable. As stated above, our pilot data indicate ubiquitous smart phone use among potential study participants.

Control Condition

The control group will participate in the same usual clinical care for diabetes (e.g., visits with primary care physician, nurse, diabetes educator, dietitian, etc.) as the intervention group. We will control for study coordinator attention time throughout the enrollment and measurement activities. The control group will be offered the digital storytelling intervention package after the study is completed.

Measures

Participant data will be collected at baseline, six weeks, three months, and six months in their preferred language. Biometric measurements will be obtained during clinic visits at baseline and 3 months. The 3 month visit can occur up to 2 weeks prior to the visit due date and up to 4 weeks after the visit due date, to accommodate scheduling limitations during the COVID-19 outbreak. Participants will complete a survey (administered by same language-congruent study staff) to obtain secondary outcomes and theory-based measures (Table 2) at clinic visits or by phone within 2 weeks following the clinic appointment, and during phone calls at 6 weeks and 6 months. Surveys will be verbally administered to participants by bilingual research staff, and responses will be entered directly into an electronic database. Surveys are not printed and given directly to the participants to complete on their own. Participants will also receive appointment reminders (three total) prior to visits or calls.

Additional clinical data will be collected from the electronic medical records. Investigators and data analysts will remain blinded to group assignment throughout the study.

Demographic, health status, acculturation, health literacy, and diabetes knowledge measures. At baseline, study participants will report on the following demographic data: sex, age, ethnicity, country of birth, annual household income, education level, employment status and housing security. Individuals will report on the following proxies for acculturation: time lived in the U.S., primary language spoken at home, and level of English language proficiency on a 5-point Likert scale¹⁰⁷. Health literacy will be measured with the Short Assessment of Health Literacy—Spanish and English¹⁰⁸. Diabetes knowledge will be measured using the Diabetes Knowledge Questionnaire, available in Spanish and English¹⁰⁹.

The following data will be obtained at baseline from manual abstraction of the electronic medical records: date of diabetes diagnosis, diabetes medications, diabetes microvascular complications (nephropathy, retinopathy, neuropathy), and presence or absence of provider-assigned diagnoses of coronary artery disease, cerebrovascular disease, peripheral arterial disease, and hypertension.

Primary outcome measure. The primary outcome measure will be glycemic control as measured by hemoglobin A1c. The rationale for use of hemoglobin A1c as an indicator of diabetes control is based on national and regional data that demonstrate significant disparities in reaching hemoglobin A1c targets for Hispanic populations compared with non-Hispanic whites^{27,110}. The importance of glycemic control as part of the comprehensive management of diabetes is well documented, and hemoglobin A1c testing is a well-established strategy to monitor glycemic control in patients with diabetes¹¹¹. Hemoglobin A1c will be measured from whole blood samples obtained and analyzed in a blinded fashion by the clinical laboratories at Hennepin Healthcare and MPHIC; both laboratories use methods certified by the National Glycohemoglobin Standardization Program. Both laboratories are certified by the College of American Pathologists.

- Baseline hemoglobin A1c values will be drawn at the baseline study visit, abstracted from the electronic medical records, or reported from an self-check A1c test kit. A1c values drawn up to two weeks prior to the baseline visit date as part of usual clinical care may be used as the baseline A1c value.
- Hemoglobin A1c values at 3 months (primary outcome) will be drawn at the 3 month study visit, or abstracted from the electronic medical records, or reported from an self-check A1c test kit. A1c values drawn up to two weeks prior or 4 weeks after the 3 month visit date as part of usual clinical care may be used as the baseline A1c value.
- Hemoglobin A1c values at 6 months will be abstracted from the electronic medical records at both institutions. A1c levels drawn 5-7 months after the baseline value will be recorded.

Secondary outcome measures. Diabetes self-management behaviors will be assessed with the Summary of Diabetes Self-Care Activities Measure (SDSCA)¹¹². This is a brief survey instrument to assess the following domains: general diet, specific (diabetes) diet, physical activity, diabetes medication use, and blood glucose monitoring. In a 2009 review of psychometric tools to assess diabetes self-management behaviors, the SDSCA was one of only three instruments to meet all appraisal criteria¹¹³. The SDSCA is also the most commonly used instrument for these domains worldwide, with good validity evidence in several languages, including Spanish^{114,115}. Furthermore, we used this instrument with Hispanic/Latino patients during the early phase (Step 1) for this project²². The SDSCA will be administered by the same language-congruent study staff at each measure.

Seated blood pressure measurements (systolic and diastolic) will be made on the right arm using an automated BP Tru BPM-200 device after sitting quietly for five minutes¹¹⁶. Blood pressure will be measured three times; the average of the second and third readings will be used in statistical analyses. Most recent values may also be abstracted from the electronic medical records.

Weight will be measured to the nearest 0.1 kg using a single portable scale (Seca 880 Digital Floor Scale). Height will be measured to the nearest 0.1 cm at baseline only using a stadiometer. Participants will be asked to remove shoes prior to both measurements. Body mass index (BMI) is calculated as weight (kg)/height squared (m²). Most recent values may also be abstracted from the electronic medical records.

Total cholesterol, HDL cholesterol, and triglycerides will be measured from the same blood sample used to derive the outcome measure. LDL-cholesterol will be calculated for each participant based on these values: LDL-cholesterol=total cholesterol – HDL cholesterol – (triglycerides/5).

- Baseline LDL-cholesterol values will be drawn at the baseline study visit. LDL-cholesterol values drawn up to two weeks prior to the baseline visit date as part of usual clinical care may be used as the baseline LDL-cholesterol value. Recent values recorded as part of usual clinical care within a week prior to the study visit may be abstracted from the electronic medical records.
- Cholesterol values at 3 months will be drawn at the 3 month study visit. Recent values recorded as part of usual clinical care within two weeks prior to the visit may be abstracted from the electronic medical records.
- Subsequent cholesterol levels will not be drawn or abstracted.

The total volume of whole blood drawn from each participant will be approximately 8 mL (3 mL for hemoglobin A1C testing and 5 mL for cholesterol testing) when visiting the lab. Over-the-counter A1c Test kits will be mailed to patients unable to visit the lab. Study staff will call patients to confirm reception of kit and go through the instructions.

All study tasks can be completed in-person in the clinical setting, virtually, or a combination of both, to accommodate the growing interest of patients to perform tasks virtually, when possible. This flexibility is noted in the Study Tasks Table below.

The number of diabetes-related office visits will be abstracted from the electronic medical records and categorized as a visit with a primary care provider, endocrinologist, pharmacist, care manager, diabetes educator, dietician, community health worker or promotora. These visits will be recorded for the six-month interval before and after intervention (or control) delivery.

Theory-based measures. We will measure diabetes-related self-efficacy with the Diabetes Self-Efficacy Scale ($\alpha=0.85$)¹¹⁷, used in other studies with Spanish-speaking patients¹¹⁸, including one from our study team that we used to generate preliminary data for this proposal²². We will measure diabetes-related outcome expectations with the Outcome Expectancies Questionnaire¹¹⁹, and social support for diabetes with items from the Diabetes Care Profile¹²⁰, which we also used in our pilot study.

Story identification and transportation will be assessed through a 14-item scale developed by Larkey and colleagues that demonstrated very good construct validity among Hispanic, Spanish-speaking populations^{121,122}, with initial predictive validity on the transportation (emotional engagement) scale⁸⁴.

Intervention follow-up exposure. During follow-up measures, we will assess the number of times each participant viewed the digital storytelling videos and whether they viewed it with friends or family. This will provide an assessment of intervention dose for the intervention group following the supervised viewing at enrollment.

Table 2. Measures

Data Collected	Baseline	6 weeks	3 months	6 months
Demographics, health status, health literacy, and diabetes knowledge	X			
Hemoglobin A1c	X		X	X
Diabetes self-management behaviors	X	X	X	X
Systolic and diastolic blood pressure	X		X	
LDL-cholesterol	X		X	
Body mass index	X		X	
Diabetes-related healthcare utilization	X		X	X
Diabetes self-efficacy, outcome expectations, and social support	X	X	X	X
Story identification and transportation	X			
Intervention follow-up exposure		X	X	X

Study Coordinator Training and Quality Assurance

The Mayo Clinic project coordinator will work with site investigators and study coordinators to oversee training of bilingual study staff at each site. We have previously described our experience training study teams for intervention delivery among Hispanic populations⁶⁷. The project coordinator will monitor quality control of the data through review of participant forms and procedures every three months. Moreover, the study statistician will perform monthly data checks (i.e., missing data, outliers).

Treatment Fidelity

Because this work will be conducted in clinical settings, it is important to evaluate barriers and facilitators to implementation across the two primary care sites¹²³. We will evaluate subset domains of the intervention delivery construct as outlined by the recently reported NIH-sponsored framework for enhancing the value of research for dissemination and implementation¹²⁴.

In the design and conduct of this study, we have incorporated recommendations from the Treatment Fidelity Workgroup¹²⁵. An intervention guide and checklist will be developed by the study team for each intervention and control component. Likewise, a checklist will be derived for collection of follow-up measures. Site principal investigators will randomly select and attend 5% of the patient visits. Based on these observations, bi-weekly meetings will be held with the study staff at each site (via videoconference) to reinforce treatment fidelity, provide corrective feedback, and to conduct additional training if needed.

Implementation adaptation. There is increasing recognition of the need for transparent reporting on adaptations of intervention implementation to fit local contexts^{124,126}. The “core” component of the intervention for this study, i.e., viewing the video, will be standard across both sites. However, during the pilot study, we learned that the timing of intervention delivery (e.g., before or after office visit), associated visit type (e.g., during diabetes classes versus during provider visits), and recruitment procedures will vary slightly between sites. We will conduct semi-structured interviews with study staff and clinical staff at both sites to assess rationale for site-specific adaptations across each of these domains, and to further elucidate generalizable best practices for implementation of this intervention. These various conditions (timing, visit type) as well as study site will be tracked and assessed for any moderating effects.

Intervention reach and adoption. Intervention reach will be reported as the percentage of invited patients who choose to participate. The differential demographic and disease-specific characteristics of these two groups will be reported and compared. Intervention adoption will be reported as the percentage of eligible patients invited to participate at each site. These groups will likewise be compared. Site-specific differences in reach and adoption will be explored through interviews with staff at each site as described above.

Sample size considerations

Our preliminary data suggest that we may expect a moderate effect size for the intervention (25%-50% times the standard deviation). This is similar to two recent meta-analyses^{127,128} of related work that informs the effect size we can expect to observe in the proposed study. The first meta-analysis of 11 randomized trials examined the efficacy of diabetes self-management education added to usual care among Hispanic patients in primary care settings, which produced an average hemoglobin A1c reduction of 0.25 standard deviations¹²⁷. The second meta-analysis of 20 randomized trials evaluated the efficacy of diabetes self-management education among

racial/ethnic minority populations, which showed a similar hemoglobin A1c reduction of 0.31 standard deviations¹²⁸. While these effects sizes are smaller than that of our pilot study, we have picked the more conservative (lower) estimate of effect size to ensure ample sample size. Hence, we can expect an effect likely to be between 0.25 and 0.31 standard deviation for the type of intervention proposed. Required sample sizes for an independent samples t-test to detect these two effect sizes, assuming 80% power, a two-tailed alternative and a 5% Type I error rate, are 252 and 145 patients per group, respectively. With 200 patients per group, we will have 80% power to detect an effect size of 0.28 standard deviations via the independent samples t-test. Accounting for approximately 12% loss to follow-up, we intend to recruit 225 patients in each group, for a total sample size of 450 participants.

Data analysis plan

Aim #1: Evaluate the efficacy of a community-derived digital storytelling intervention among Hispanic adults with poorly controlled T2D.

The primary analysis will be an independent samples t-test between the group average hemoglobin A1c values at 3 months. A two-sided alternative with a 5% type I error rate will be employed.

Supplementary analysis for the primary endpoint. Repeated measures modeling of the individual time point A1c values (including chart abstracted values at approximately 6 months) will allow for a more detailed investigation to the timing of the impact of the intervention by including all time points (including baseline). Profile analysis (Srivastava) will further assess for difference in overall means, time point, and treatment by time interactions. Covariates indicated above including demographics and clinical covariates will be included in the repeated measures and profile analysis models to assess the sensitivity of the primary analysis conditional on these potential concomitant (mediating) influences.

Secondary analyses. The analyses applied to the primary endpoint will also be applied to each of the secondary endpoints. The subscales from the SDSCA (general diet, diabetes diet, physical activity, diabetes medication use, blood glucose monitoring) and the physical measurements (blood pressure, LDL-cholesterol, BMI) will be compared between groups using t-tests and repeated measures monitoring similar to the primary endpoint. As we have a *single variable* primary endpoint defined, there will be no adjustment for comparison-wise Type I error rate. Additional analyses will be performed to identify potential effect modifiers for the primary and secondary outcomes, i.e., sex, age, socioeconomic position, acculturation, health literacy, and diabetes knowledge.

Aim #2: Explore the effect of the digital storytelling intervention on proposed theory-based mediators of change.

We will examine the correlational structure of the covariates and their impact on the intervention effect size via repeated measures models. We will include procedures suggested by MacKinnon^{129,130} to assess mediation, fitting three general estimating equation models to the data. We will first estimate the intervention effect separately for the dependent variable (with regression adjustment for covariates); that model provides an estimate of the total effect of the intervention. Next, we will estimate the intervention effect for each mediator (with regression adjustment for covariates); that model provides an estimate of the effect of the intervention on the mediator. Finally, we will estimate the mediated intervention effect for the dependent variable by adjusting for the mediator (and covariates); that model provides an estimate of the unmediated (i.e., direct) intervention effect, and the intervention-adjusted effect of the mediator on the dependent variable. These analyses will be done for the primary endpoint and each of the secondary endpoints to identify any mediators of the study results.

Table 3. Study Timeline

Tasks to be completed	Year 1	Year 2	Year 3	Year 4
Recruitment, enrollment, and baseline measures				
Intervention				
Follow-up measurements				
Data analysis				
Dissemination and sustainability plan				

Dissemination and Sustainability Plan

Consistent with CBPR principles¹⁰, dissemination of research findings will be a collaborative, multi-modal effort by both academic and community partners following the same process established with prior RHCP research efforts. Dissemination will occur at RHCP meetings, community meeting places, at academic conferences, and in peer-reviewed publications. Presentations and authorship will be shared by community, clinical and academic partners.

Sustainability of successful components of the program will be a high priority. Consistent with previous RHCP efforts, sustainability planning will occur with community members. Small group brainstorming sessions will commence even before data analysis is completed. This will be an iterative process using results from brainstorming sessions to inform subsequent discussions until a collaborative plan is in place. The intervention is intentionally designed to be sustainable and scalable. The behavioral messages contained in the stories (dietary quality, physical activity, medication adherence, glucose self-monitoring) are unlikely to lose clinical relevance over time. Once effectiveness is established, the intervention will be housed online in the public domain and available as a mobile application for use in clinical settings across the country. Furthermore, the process of participatory digital storytelling intervention development contained in this work will provide a flexible template to address other health issues among diverse subset populations. This template incorporates the digital storytelling CBPR process for message development and model factors to emphasize in selecting stories to share. Furthermore, these products may be added to other evidence-based diabetes technologies to examine effectiveness of mobile applications for diabetes self-management among diverse populations.

Potential Problems & Alternative Strategies

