Once eligible patients are identified from institutional registries, the next office appointment for any diabetes-related indication (e.g., chronic disease management provider visit, diabetes educator visit, dietitian visit, diabetes group class, etc.) will be recorded for each patient. These patients will be contacted by telephone by a language-congruent study staff member to introduce them to the study and to assess preliminary interest in participation. Patients will be sequentially recruited at their next office visit until the target accrual is reached. Patients may also be recruited, consented and participate in study activities over the phone.

A language-congruent study staff member will confirm eligibility criteria with the patient and obtain written informed consent in an exam or private room before or immediately after their office appointment. Study staff will then obtain a baseline survey and biometric assessment (see measures) followed by randomization procedures (stratified by gender) and delivery of the digital storytelling intervention (for the intervention group). Each site has developed slightly different protocols for effective recruitment and intervention implementation based on lessons learned from the pilot study. Based on data from our pilot, we expect recruitment and enrollment to occur over a period of no more than 24 months across all sites with the following distribution:

- Hennepin Healthcare: N=240 participants enrolled.
 - Medicine Clinic
 - East Lake Clinic
 - Richfield Clinic
- Mountain Park Health Center: N=215 participants enrolled.

Participant retention will be facilitated in five ways. First, potential participants will confirm the eligibility criteria stating that they expect to receive medical care at the recruitment clinic for at least the next six months (above). Second, appointment cards for both subsequent study visits will be provided to participants after they have completed enrollment. Third, language-congruent study staff will contact patients by phone to remind them about upcoming study visits. Fourth, participants who do not return phone calls from study staff will be sent a letter asking them to call the study coordination to reschedule the appointment. Fifth, participants will receive remuneration at enrollment and at the of the 3 month visit.

Interventions

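### The primary t-test on 3-month A1c leaves out gender, the named stratification factor, and site; adding both gives a correctly sized test and a small gain in precision

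*Combined protocol and SAP*

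**What the plan says.** The section on recruitment, enrollment, randomization and retention places "randomization procedures (stratified by gender" after the baseline assessment and before the video is shown. Gender is the only factor named. The documents do not describe how the allocation list is generated or whether each site has its own. The same section plans 240 participants at Hennepin Healthcare and 215 at Mountain Park Health Center.

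Under Aim #1 of the data analysis plan, "The primary analysis will be an independent samples t-test between the group average hemoglobin A1c values at 3 months". It adds: "A two-sided alternative with a 5% type I error rate will be employed". No covariate is named for this test.

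Sex and site appear elsewhere:
- Demographic covariates, which include sex, enter the supplementary repeated-measures and profile models.
- Sex is listed as a possible effect modifier under the secondary analyses.
- Under implementation adaptation, delivery timing and visit type "as well as study site will be tracked and assessed for any moderating effects". Site is not in the list of demographic measures.

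**The concern.** When randomisation is stratified on a factor related to the outcome, the treatment estimate varies less than it would under simple randomisation. An analysis that ignores the factor does not see this. It reports a standard error that is too large, so the test rejects less often than its nominal level and part of the benefit of stratifying is lost.

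Site raises a different question. The two institutions are a public academic system in Minneapolis and a community health center in Phoenix. Each has its own laboratory, and recruitment and delivery procedures differ slightly. If 3-month A1c differs between them, that variance stays in the error term of the t-test, although site is known for every participant.

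Precision is at stake, not validity. It has some value here because the sample size has no slack: 200 per group gives 80% power at 0.28 SD, and the protocol itself puts the likely effect between 0.25 and 0.31 SD.

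**Working it through.** **Inputs from the documents.** 200 evaluable per group, 0.28 SD, two-sided 5% (sample size considerations); site sizes 240 and 215; about 50% women expected (study participants).

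**Assumed.** The documents give no difference in 3-month A1c between sexes or sites. I take D = 0.2, 0.3 and 0.5 SD for each, the two factors unrelated, and the same treatment effect in every stratum. SD means the total SD, as in the sample size section.

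**1. The plan's own figure.** The protocol states "With 200 patients per group, we will have 80% power to detect an effect size of 0.28 standard deviations". The exact two-sample t-test gives 79.8%, and the normal approximation gives 80.0%. The figure reproduces.

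**2. Sex: balanced by design, ignored in the analysis.** With half the sample women, sex explains R² = 0.5 × 0.5 × D² of the variance. The true variance of the estimated difference, in SD units, is (1 − R²) × 2/200, but the t-test uses about 2/200. The true type I error is therefore 2 × [1 − Φ(1.96/√(1 − R²))].

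| D (assumed) | R² for sex | True type I error |
|---|---|---|
| 0.2 | 0.010 | 4.9% |
| 0.3 | 0.0225 | 4.7% |
| 0.5 | 0.0625 | 4.3% |

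**3. Site: chance imbalance if allocation is not by site.** The site share is p = 240/455 = 0.527. The difference between arms in that share has SD √(p(1 − p) × 2/200) = √(0.2492 × 0.01) = 0.050, or 5.0 percentage points (95% range ±1.96 × 5.0 = ±9.8 points). Multiplied by D = 0.2, 0.3 or 0.5, the 95% range corresponds to a shift of ±0.020, ±0.029 or ±0.049 SD. This is a component of the ordinary 95% margin, 1.96 × √(2/200) = ±0.196 SD, and not an addition to it.

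**4. Gain from adjustment.** Site explains p(1 − p)D² of the variance. Power is recomputed at 0.28/√(1 − R²) with 200 per group, using R² for site alone or the sum for site and sex.

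| D (assumed, each factor) | Power, site only | Power, site and sex | n per group for 80%, site and sex |
|---|---|---|---|
| none | 79.8% | 79.8% | 201 |
| 0.2 | 80.2% | 80.6% | 197 |
| 0.3 | 80.7% | 81.5% | 192 |
| 0.5 | 82.2% | 84.8% | 176 |

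The 79.8% starting point slightly understates the planned test when sex matters. With sex balanced, the unadjusted t-test has power of about 80.1%, 80.2% or 80.7% at D = 0.2, 0.3 or 0.5 (normal approximation, against 80.0% with no sex difference). The true gain is smaller than the table suggests by 0.1 to 0.7 points.

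**The case against.** The other side has a good case that this is small, and several stronger readings do not hold.

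- A reader might infer that between-sex variation stays in the estimate. It does not, because stratification balances sex. Only the standard error is affected, and in the conservative direction.
- A reader might infer that adjusting for site corrects the standard error. If allocation is not by site, chance site imbalance is ordinary randomisation error and the t-test already counts it. The standard error is then correct and the estimate unbiased, so adjustment only adds precision.
- A reader might set the shift of up to 0.049 SD against the 0.28 SD target and call it a distortion. It is a 95% extreme, rests on an assumed site difference, and already lies inside the margin of error.
- A reader might infer that the site-moderator analysis needs balanced arms. An interaction is validly estimated with unequal arms. A split of 130 to 110 among the 240 at Hennepin keeps 4 × 130 × 110/240² = 99.3% of the efficiency.
- A reader might take it as established that allocation ignores site. The documents only fail to name site, and separate lists per site remain possible. If they exist, site is also balanced by design and the argument for sex extends to it: with both factors balanced and ignored, type I error would be about 4.8%, 4.5% or 3.6% at D = 0.2, 0.3 or 0.5.

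The documents also give reasons to expect small site differences. Both laboratories use NGSP-certified methods, both sites apply the same A1c entry threshold of 8%, and the protocol describes procedures as varying only slightly. Values may also come from records or self-check kits, so site is not a clean marker of assay. Sex already enters the supplementary models.

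What stands is that the supplementary models do not change the primary test, that this test omits the factor used to randomise, and that site is not named as a covariate in any model.

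**Conclusion.** The point holds as a minor improvement. The planned t-test controls type I error and is unbiased. It is slightly conservative because it ignores gender, with a true level of 4.3% to 4.9% over the assumed range, and it leaves any between-site variance in the error. Adjusting for both factors adds about 1 power point at assumed differences of 0.2 SD and about 5 at 0.5 SD; site alone adds 0.4 to 2.4 points.

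These sizes depend wholly on differences that the documents do not give. The certified laboratory methods and common entry threshold make the low end more plausible. No conclusion of the trial is threatened.

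**What to change.** Before unblinding, specify the primary 3-month A1c analysis as a linear model with treatment, sex and site (the two institutions) as fixed effects, tested two-sided at 5%. Keep the independent samples t-test as a sensitivity analysis. The same model can serve the secondary outcomes, which follow the primary analysis.

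Optionally, state in the randomisation section whether allocation lists are kept by site.

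The cost is a few lines of analysis-plan wording and two degrees of freedom out of about 400. Sex and site are already recorded, and the required sample size does not rise.
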